### 10.2.1 Additional Sources for Data Collection

To complete the data obtained from pharmacies and medical practices, there are also other sources to obtain information e.g., about events. Health insurance funds (Statutory Health insurance (SHI) and private) are asked for information, as well as German data processing centres (*Apothekenrechenzentren*) and comparable resources, e.g. registration offices (*Einwohnermeldeämter*) or health offices. All data will be kept in safe and confidential custody at IZKS Mainz.

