### 11.5.3 Exclusion Bias

Potential bias:

Patients of the intervention group may stop following the study protocol because they do not want to visit the pharmacy as frequent as required or because they do not like the weekly dosing aids.

→ Intention-to-treat-analysis

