Table 4 PDC analyses - definition for 365 days' follow-up

	Intervention group (IG) and control group (CG)
ITT	Version 1) From randomization until 365 days following the randomization If a patient dies: the sum of days between randomization and date of death Version 2) If a patient discontinues within 365 days: the sum of days between randomization and discontinuation

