5.7 Primary safety variable

The primary safety variable is all-cause mortality or unplanned cardiovascular hospitalizations as days lost due to unplanned cardiovascular hospitalizations or death of any cause between baseline (day of randomization) and 365 days. For death, the remaining days to 365 days will be counted. The days spent in hospital will be added to the days after death until 365 days.

The percentage of days lost due to hospitalisation and death will be calculated as the ratio of the sum of the number of days lost due to death and spent in hospital during the 365-days follow-up and the respective patient follow-up time, expressed in percent.

If a patient terminated the study within 365 days, the days lost between the day of randomization and the day of discontinuation will be analysed accordingly.

For days lost due to unplanned cardiovascular hospitalizations, the admission und discharge day will be counted as one day. Calculations will be done in days.

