5.9 Secondary safety variables

The following secondary safety outcomes will be evaluated during 365-days follow-up according to the primary safety variables:

- Percentage of days lost due to unplanned cardiovascular (CV) hospitalizations or all-cause death
- All-cause mortality or unplanned cardiovascular hospitalizations as recurrent event (number)
- Unplanned cardiovascular hospitalizations (recurrent event, number)
- Unplanned hospitalizations for heart failure (recurrent event, number)
- Days lost due to hospitalizations of any cause or death
- Percentage of days lost due to hospitalizations of any cause or death of any cause
- Unplanned all-cause hospitalizations
- All-cause mortality

The following secondary safety outcomes will be evaluated during the patient's individual time within study (=individual follow-up time):

- All-cause mortality or unplanned cardiovascular hospitalizations as recurrent event (number)
- Unplanned cardiovascular hospitalizations (recurrent event, number)
- Unplanned hospitalizations for heart failure (recurrent event, number)
- Percentage of days lost due to unplanned cardiovascular hospitalizations
- Percentage of days lost due to hospitalizations of any cause
- Unplanned all-cause hospitalizations

- All-cause mortality

Table 5 Secondary safety variables - Definition of patients' individual follow-up time

	Intervention group (IG) and control group (CG)
ITT	From randomization until end of study. End of study: 
 - 31.12.2016 - If date of visit 6 or last visit in 2017: 31.12.2016 - If date of final study visit before 30.06.2016: Date of visit 6 - Death: date of death - Withdrawal of informed consent: date of withdrawal - Premature termination of study: date of premature termination

The percentage of days lost due to hospitalisation will be calculated as the ratio of the sum of the number of days lost due to stays in hospital during the respective patient follow-up time and the respective patient follow-up time, expressed in percent.

For days lost due to unplanned cardiovascular hospitalizations, the admission und discharge day will be counted as one day. Calculations will be done in days.

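### Primary safety follow-up stops at study discontinuation even for patients who keep consent, so a later death or cardiovascular admission adds no days lost; 3 of 237 ITT patients are affected in year 1

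*SAP*

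**What the plan says.** **Window and cut.** SAP 5.7 runs the primary safety variable from randomization to day 365. Deaths are carried to the end of the window: "For death, the remaining days to 365 days will be counted". For early terminators the count stops sooner: "If a patient terminated the study within 365 days, the days lost between the day of randomization and the day of discontinuation" are analysed on the same lines. Consent status plays no part in this rule.

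**Percentage.** SAP 5.7 divides days lost by "the respective patient follow-up time, expressed in percent". SAP 7.9 divides by the maximum possible days. SAP 7.9 tests the percentage and only describes the number of days.

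**Individual follow-up.** Table 5 in SAP 5.9 closes follow-up the same way: "Premature termination of study: date of premature termination". The time-to-event analyses in SAP 7.10.2 instead censor at last contact.

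**Adherence.** Table 4 in SAP 5.6 gives the PDC two windows. Version 1 runs "From randomization until 365 days following the randomization", or to death. Version 2 stops at discontinuation. Neither is named primary.

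**Sources.** Only withdrawal of consent is said to block external data (SAP 5.4.1 and 5.5, Protocol 11.3). Insurers are asked about hospitalizations at the end of the study (Protocol 8.3, SAP 5.4.1). Protocol 10.2.1 adds "comparable resources, e.g. registration offices". Table 3 in SAP 2.3 lists discontinuation separately from withdrawal of consent.

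**The concern.** The cut departs from the variable's own 365-day definition, and the documents give no reason for it where consent still stands. For these patients the plan already names places to look for later events, yet such events could not enter the primary safety result. The PDC has a version that keeps discontinued patients to day 365; the safety variable has no counterpart.

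Protocol 11.5.3 lists as a bias that "Patients of the intervention group may stop following the study protocol", and offers intention-to-treat analysis as the remedy. Stopping the outcome count at discontinuation is not that analysis. If discontinuation were linked to prognosis, serious outcomes would leave the comparison, possibly unequally between arms.

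**Working it through.** **1. Reproduce the counts (SAP Tables 2 and 3).**
- ITT: 130 − 17 − 3 = 110 intervention; 128 − 0 − 1 = 127 control; total 237.
- Terminated within 12 months: 8 = 6 withdrew consent + 2 discontinued (intervention); 2 = 1 + 1 (control); 10 = 7 + 3 in total.
- PP: 110 − 8 = 102; 127 − 2 = 125; total 227. All agree with the SAP.

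The patients who could still be followed are the 3 who discontinued without withdrawing consent: 2/110 = 1.8%, 1/127 = 0.8%, together 3/237 = 1.3%. The other 7 withdrew consent and are untouched by this point.

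**2. What the rule does to one patient (illustrative days).** A consenting patient stops at day 100 with no earlier event and dies at day 120.
- 365-day definition: 365 − 120 = 245 days lost, or 245/365 = 67.1%.
- Rule as written: 0 days; 0/100 = 0% on own follow-up time and 0/365 = 0% on maximum possible days.

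Under either denominator this patient ties with someone who had no event all year.

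**3. The score is not always too low.** A patient stops at day 60 after 10 unplanned cardiovascular hospital days. On own follow-up time the score is 10/60 = 16.7%; on 365 days it is 10/365 = 2.7%. With the SAP 5.7 denominator, truncation can raise the tested percentage, so the rule has no fixed direction.

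**4. Upper bound on mean days lost.** Understatement is at most (number affected) × (days remaining) / (arm size).
- All stop and die near day 0: 2 × 365/110 = 6.6 days (intervention), 1 × 365/127 = 2.9 days (control).
- All stop and die at day 180: 2 × 185/110 = 3.4 and 185/127 = 1.5 days.

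**5. Effect on a rank test.** The documents give no event rate, so 60% to 90% of patients were assumed to have zero days lost. Restored deaths were given 335 days lost, and the change in a tie-corrected two-sample rank-sum z was averaged over 400 simulated data sets with arms of 110 and 127. Positive means more days lost with the intervention.

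| Restored deaths | Shift in z |
|---|---|
| Both intervention patients | +0.38 to +0.49 |
| Control patient only | −0.16 to −0.21 |
| All three | +0.22 to +0.28 |

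**6. How likely is any hidden event?** Assume a one-year event probability p of 10% to 40% and half a year remaining. The expected number among the three is 3 × (1 − (1 − p)^0.5): 0.15 at p = 10% and 0.68 at p = 40%.

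**The case against.** The strongest reply is that very little is at stake. Three patients are affected, split 2 v 1, and the expected number with any hidden event is below one under the assumed rates. That stands, and it limits the weight of the point.

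The contrast with adherence is also less sharp than it looks. PDC Version 2 truncates too, and SAP 5.8.1 cuts the 730-day PDC at discontinuation. That stands as well; what remains is that safety has no day-365 version at all.

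A reader might infer that adherence and hospital data come from the same insurers, so that following one shows the other is feasible. The documents do not support this. Dispensing data come from data processing centres with insurers in addition (SAP 5.5), and insurer data were not available for all patients (SAP 7.8). Insurers are asked about hospitalizations; registration offices are named only as an example.

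Protocol 11.5.3 concerns patients who tire of pharmacy visits or dosing aids. Someone who stops collecting dosing aids but remains in the study is not cut by SAP 5.7. That section supports the principle but does not describe the three patients here.

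For Table 5, the count models use time in study as an offset and the mortality analysis censors. Early termination there shortens observation; it does not create a zero score. Those analyses are exploratory (SAP 7.10).

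**Conclusion.** The point holds as a consistency fault in the primary safety variable that is cheap to correct. As written, SAP 5.7 discards any death or unplanned cardiovascular admission after discontinuation, even with consent in place and a source named in the plan. In year 1 this concerns 3 of 237 ITT patients. The extreme bound is 6.6 v 2.9 mean days understated; the likely effect is much smaller and would not by itself be expected to drive the result. Discontinuations after month 12 also bear on individual follow-up, but their number is not given.

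Two stronger readings should be resisted. A reader might infer that later deaths are known and are being scored as zero; no passage shows that any such event occurred or was reported. A reader might also infer that the safety result leans towards the intervention. The reasons for the three discontinuations and their later outcomes are not given, a difference of one patient between arms is no evidence of direction, and step 3 shows the percentage can move either way.

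The size rests on Table 3 being complete for year 1; the rank-test and expected-event figures rest on assumed event rates.

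**What to change.** - **SAP 5.7:** end safety follow-up early only at withdrawal of consent. For other discontinuations, count deaths and unplanned cardiovascular hospitalizations to day 365 where insurer, practice or registration-office data exist. Where no such source exists, count to last contact. Keep the truncated version as a sensitivity analysis, as Table 4 does for the PDC.
- **SAP 5.7 and 7.9:** state one denominator for the percentage.
- **Table 4:** say which PDC version is primary.
- **Table 5:** extend follow-up of consenting discontinuers to the common end date where data exist, and reconcile it with the last-contact censoring in SAP 7.10.2.

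The cost is a few sentences and a few extra lookups through sources the protocol already lists. Without insurer data, hospitalizations will still be counted only to last contact for some patients, so the longer window will not be equally complete for everyone.

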5.8 Secondary efficacy variables

5.8.1 Adherence to medication

We will analyse the PDC during the 365-days follow-up for each drug class (ACEi/ARB, BB, MRA), percentage of patients with a mean PDC $\geq 80\%$ (=adherent), and percentage of patients with a PDC $\geq 80\%$ for each drug class (sensitivity analyses for a cutpoint $\geq 88\%$). In addition, we will perform the different types of calculating the PDC between baseline and 730 days.

If a patient discontinues within 730 days, the days between randomization and the day of discontinuation will be analysed. Days after death will be censored.

We will analyse the PDC for lipid modifying agents accordingly (at baseline, during 365-days follow-up, during 730-days follow-up, percentage of patients with a mean PDC $\geq 80\%$ (=adherent; sensitivity analyses for a cutpoint $\geq 88\%$).

The different calculations of the PDC will be performed by the pmv research group.

It will be checked, if the PDC data are suited for a non-parametric approach by checking the histogram for the distribution of the PDC data. If the PDC are not suited for a parametric / non-parametric analysis approach, categorization of the data will be considered.

5.8.2 Quality of Life (QoL)

Change in MLHFQ -questionnaire overall score between baseline and 365 days (main secondary outcome) and between baseline and 730 days (other secondary outcome). The Minnesota Living with Heart Failure (MLHF) questionnaire will be filled out at screening, visit 3 (after 12 months), and visit 5 (after 24 months). The MLHF is specific for chronic heart failure and consists out of 21 items which are scored on a 6 point Likert-scale (0="not at all" to 5="very much"). Each question is about how much a special facet prevented the patient from living as desired. The total score is calculated as the sum over all non-missing items and ranges from 0 to 105: higher scores indicate worse QoL. A score of < 24 signifies a good, a score between 24 and 45 signifies a moderate, and a score > 45 signifies a poor QoL.

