## 10.3 Data Handling

During data entry, integrity checks help to minimize entry failures. These data entry checks are defined in the data validation plan. The data entry system allows the study monitors to control the entry process with the help of the system-own review functions. Comments and requests can be processed by the study site just in time.

During the study, data is exported into the statistical analysis system (SAS) and checked additionally for plausibility, consistency and completeness. Based on these checks, queries are produced. Any missing data or inconsistencies are reported back to the respective site and clarified by the responsible investigator. If all corrections are done, the database is closed and used for statistical analyses.

All collected data will be processed according to the German Data Protection Law and handled in strictest confidence. To cover all relevant aspects of data protection a data protection commissioner is involved. A Data-Safety concept will be implemented and specified in a separate document. The latter will be prepared in cooperation with and handed in for approval to the data protection commissioner. Personal data will be strictly separated from the study database.

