5.3 Demographics and patient characteristics

The following demographic variables will be documented at screening / visit 1:

- Sex (male / female)
- Date of birth
- *Derived: Age [years] = Date of screening – date of birth*
- *Derived: Age will also be categorized as ≤ 75 years and > 75 years*
- Height (cm)
- *Derived: BMI = weight [kg] / (height [cm] / 100)²*
- *Derived: The BMI will also be categorized as underweight (< 18.5 kg/m²) / normal (between 18.5 kg/m² and 25 kg/m²) / overweight (≥ 25 kg/m²)*

The following baseline characteristics will be documented at screening / visit 1:

- Informed consent available (yes/no)
- In- and exclusion criteria
- Randomization result
- Main reason for chronic heart failure (ischaemic, non-ischaemic, other)
- Date of first diagnosis of chronic heart failure (month/year)
- *Derived: Time since first diagnosis [years] = date of screening - date of first diagnosis of chronic heart failure (month/year)*
- Date of last hospitalization due to acute cardiac decompensation
- *Derived: Time since last hospitalization [years] = date of screening - date of last hospitalization due to acute cardiac decompensation*
- *Derived: The time since the index hospitalization will be classified as < 3 months and ≥ 3 months*
- Left ventricular ejection fraction (LVEF, %) at baseline, if available. The LVEF will also be categorized as $< 40\%$ indicating HF_rEF, 40% - 49% indicating HF_{mr}EF, $\geq 50\%$ indicating HF_pEF

The following characteristics will be documented at visits 1, 3, and 5:

- Weight (kg)
- Blood pressure (systolic blood pressure, diastolic blood pressure [mmHg])
- Pulse at rest [/min]
- Care level (Pflegestufe; none/1/2/3/missing/unknown)
- Attendance at Disease Management Program (DMP) KHK (yes/no)
- Attendance at DMP KHK – module heart failure (yes/no)
- Heart pacemaker incl. ICD/CRT (yes/no/unknown) (if yes, with or without a defibrillator)
- New York Heart Association Functional Classification (NYHA class I, II, III or IV)
 - *Derived: The NYHA class will also be categorized as I/II and III/IV.*
- Smoking status (smoker, non-smoker, former smoker)
- Minnesota Living with Heart Failure Questionnaire (MLHFQ) (total score)
 - *Derived: physical and emotional sub-scores, total score at baseline will be categorized as < 24, between 24 and 45, > 45)*
- Patient Health Questionnaire PHQ-9 (total score)
 - *Derived: The PHQ-9 total score at baseline will be categorized as < 10 and ≥ 10*

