5.8.4 Patient Health Questionnaire (PHQ-9)

Change in depression measure by the Patient Health Questionnaire (PHQ-9D = validated German version of the PHQ-9) between baseline and 365 days (main secondary outcome) and between baseline and 730 days (other secondary outcome). The PHQ-9D will be filled out at screening, visit 3 (after 12 months) and visit 5 (after 24 months). The PHQ-9D is a self-administered version of the PRIME-MD diagnostic instrument common mental disorders. The PHQ-9 is the depression module, which scores each of the 9 DSM-IV criteria. It has been validated for use in primary care. The PHQ-9D questionnaire will be analysed by assigning 0 point for the category “never”, 1 point for the category “at some days”, 2 points for the category “at more than 50% of the days” and 3 points for the category “nearly every day”. The total score will be calculated building the sum of all items and therefore ranges between 0 and 27. The cut-off for signs of depression was set at a PHQ-9 score of ≥ 10 .

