6.1 Missing values

No substitution of missing values will be done.

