6.2 Outliers

No methods for detection of outliers will be employed.

7 Statistical analyses

Categorical variables will be presented by numbers and percentages. If not otherwise stated, the missing values will be shown as an additional missing category and the percentages will be calculated based on all non-missing values.

Continuous variables will be summarised by the descriptive statistics n, mean, standard deviation, minimum, 25%-quartile, median, 75%-quartile and maximum.

All variables will be shown for each treatment group and in total.

All variables documented in the eCRF will be provided by patient in Excel datasheets.

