7.10.1.2 Quality of life (Minnesota Living with Heart Failure Questionnaire, total score)

The changes to baseline of the total score of the Minnesota Living with Heart Failure Questionnaire after 1 year and, if sufficient data are available, after 2 years will be analysed by an ANCOVA, including treatment as fixed effect and total score at baseline as covariate. Parameter estimates and adjusted mean differences (LSMEAN differences) will be shown together with their corresponding p-values and 95% confidence intervals.

Additionally, the total score as well as the corresponding change to baseline will be analysed descriptively by visit, treatment group and in total.

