7.11 Subgroup analyses

Exploratory subgroup analyses will be performed for the primary efficacy and primary safety variables. Additionally, subgroup analyses for the PDC of each drug class, the mean PDC $\geq 80\%$, all-cause mortality or unplanned cardiovascular hospitalizations as recurrent event, unplanned cardiovascular hospitalizations as recurrent event, and all-cause mortality will be performed.

Each subgroup and the corresponding interaction with treatment group will be included into the analysis model (the PDC of each drug class will be analysed by an ANOVA,

for the mean PDC $\geq 80\%$ a logistic regression model will be used). The following subgroups are planned:

- Minimization-criteria:
 - o Sex (male/female),
 - o Age (≤ 75 , > 75 years),
 - o NYHA functional class (I and II, III and IV),
 - o PHQ-9 (depression score < 10 , ≥ 10),
 - o Diabetes mellitus (yes/no),
- Time between last heart failure hospitalization and randomization (< 3 months vs. ≥ 3 months) Number of different drug substances (median at randomisation), as an indicator of the level of illness burden
- Number of different co-morbidities (median at randomisation), as a further indicator of the level of illness burden
- Heart failure medication at baseline (BB versus BB plus ACEi/ARB, BB plus ACEi/ARB versus BB plus ACEi/ARB/MRA) (subpopulations)
- Heart rate at baseline (≤ 75 vs. > 75 min^{-1})
- QoL score (MLHFQ Median)
- HFrEF vs. HFmrEF/HFpEF (LVEF $< 40\%$ vs. $\geq 40\%$)

The subgroup analyses will be displayed by the interaction term as well as descriptive statistics by subgroup.

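### The MLHFQ total in effect scores every unanswered item 0 and requires no minimum number of answers, so an incomplete form looks too good whenever a skipped item was truly above 0

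*SAP*

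**What the plan says.** SAP 5.8.2 describes 21 items, each scored 0 to 5, where 0 is a real answer (no limitation at all). It scores the form as follows: "The total score is calculated as the sum over all non-missing items and ranges from 0 to 105: higher scores indicate worse QoL". Totals below 24 are called good, 24 to 45 moderate and above 45 poor.

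No section of either document sets a minimum number of answered items, prorates, or says when the total becomes missing. The general rule in SAP 6.1 is "No substitution of missing values will be done". For categorical variables, the opening of SAP section 7 adds that "the missing values will be shown as an additional missing category".

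The total is used in four places:

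- the change from baseline at 12 and 24 months (SAP 5.8.2);
- the ANCOVA of that change, "including treatment as fixed effect and total score at baseline as covariate" (SAP 7.10.1.2; Protocol 11.4.3.2 is equivalent);
- the baseline description, where SAP 5.3 lists "physical and emotional sub-scores, total score at baseline will be categorized as < 24, between 24 and 45, > 45";
- the median split for the exploratory subgroup analyses (SAP 7.11).

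The questionnaires are completed on paper (Protocol 10.2). For the PHQ-9, SAP 5.8.4 defines the total over all items and does not restrict it to the non-missing ones, so the two questionnaires are worded differently without a stated reason.

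**The concern.** Leaving a blank out of a sum is numerically the same as entering 0 for it, and on this scale 0 is the most favourable answer. An incomplete form can therefore never score too high, and it scores too low whenever a skipped item was truly above 0.

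The rule also makes incompleteness invisible. A partly answered form always produces a total, so it counts in the n, falls into a quality-of-life band and is not displayed as missing. Neither document plans a count of unanswered items, although SAP section 10 places the planned tables in a separate document that is not available here.

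At stake is the quality-of-life comparison. If the arms differ at V3 or V5 in how many items are skipped, or in the true values of those items, part of the observed difference comes from the scoring rule. If they skip alike, a true difference is shrunk.

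**Working it through.** **1. Inputs.** From SAP 5.8.2: 21 items, item range 0 to 5, cut-offs 24 and 45. From SAP 7.10.1.2: ANCOVA of change with the baseline total as covariate. Not in the documents: the number of skipped items, their true values, and any difference between arms. Every size below is conditional on an assumed value.

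**2. The plan's own range.** 21 × 0 = 0 and 21 × 5 = 105, so the stated range is reproduced, but only for complete forms. With k blanks the highest possible total is 5 × (21 − k): 100 for k = 1, 85 for k = 4, 55 for k = 10, 5 for k = 20. From k = 17 the maximum is 5 × 4 = 20, below 24, so such a form is banded good whatever the patient's state.

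**3. Error of one form.** Let m be the mean of the answered items and v the true mean of the k skipped ones. The true total is (21 − k)m + kv.

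- Raw sum (21 − k)m: error −k·v.
- Prorated score 21m: error k·(m − v).
- Proration is closer to the truth when v > m/2; the raw sum is closer when v < m/2.

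**4. Example (assumed).** 18 items answered, sum 43, three skipped. Then m = 43/18 = 2.39, m/2 = 1.19, raw total 43 (moderate), prorated 43/18 × 21 = 50.2 (poor).

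| True sum of the 3 skipped items | True total and band | Raw error | Prorated error |
|---|---|---|---|
| 0 | 43, moderate | 0 | +7.2 |
| 2 | 45, moderate | −2 | +5.2 |
| 3 | 46, poor | −3 | +4.2 |
| 4 | 47, poor | −4 | +3.2 |
| 15 | 58, poor | −15 | −7.8 |

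The raw band is wrong from a skipped sum of 3 upward; the prorated band is wrong at 2 or less. The example lies close to the 45 cut-off, which is why the band changes so easily.

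**5. Individual change score.** A patient truly at 50 at both visits who skips three items of average value scores 50 × 18/21 = 42.9 on that form. The apparent change is +7.1 if the skips are at V1 and −7.1 if they are at V3.

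**6. What reaches the treatment estimate.** The planned model is V3 − V1 = a + b·treatment + c·V1. Moving V1 to the right gives V3 = a + b·treatment + (c + 1)·V1, with the same b. A V1 error therefore acts only through the covariate. If V1 skips precede allocation they are balanced in expectation and mainly cost precision. SAP 5.8.2 places the baseline form at screening. Protocol 8.2.1 mentions allocation before the questionnaires and lets screening, randomization and V1 share one visit, so the order is not firmly fixed.

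**7. Difference between arms at V3.** With V1 skipping balanced, the shift is the difference between arms in mean k·v.

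- A mean difference of 0.5 skips of average value T/21: 0.5 × 24/21 = 0.6; 0.5 × 45/21 = 1.1; 0.5 × 60/21 = 1.4 points, at mean true totals T of 24, 45 and 60.
- One skip per form in both arms, with true means of 1 and 3 for the skipped items: 1 × (3 − 1) = 2 points.

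**8. Equal skipping.** With s average-value items skipped per form in both arms, a true difference is multiplied by 1 − s/21: 0.952 for s = 1 and 0.857 for s = 3, a loss of 5% to 14%.

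**The case against.** The strongest reply is that SAP 5.8.2 does not leave a gap. It fixes in advance how incomplete forms are scored, and the alternative has its own error. Step 3 shows that proration is further from the truth when the skipped items' true mean is below half the answered mean, and the documents do not say which case applies. This stands, and it is why the raw sum should remain as a sensitivity analysis. It does not explain why a form with one answer out of 21 should be scored at all.

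A reader might infer that the rule contradicts SAP 6.1, and that 6.1 therefore calls for proration. The documents do not support that. Summing what was answered respects the wording of 6.1 even though it equals entering 0, and proration is itself a substitution that needs an exception to 6.1.

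A reader might also take the 7.1 points in step 5 as a bias in the treatment comparison from V1 skips. Step 6 shows that it is not: it describes an individual or descriptive change.

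Three further replies carry some weight. Protocol 10.3 provides that "Any missing data or inconsistencies are reported back to the respective site and clarified by the responsible investigator", so some blanks may be recovered, although queries go to the site while the answers are the patient's. A table of unanswered items may exist in the separate tables document. And the stakes are limited: SAP 7.10 treats secondary p-values as exploratory, Protocol 11.1 powers the study for primary efficacy only, and SAP 5.8.4 gives the PHQ-9 the same main-secondary label.

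**Conclusion.** The point holds as a minor one. It is certain by arithmetic that the rule equals scoring blanks as 0, that it understates the total whenever a skipped item was truly above 0, and that nearly blank forms receive a total and a good band. The effect on this trial's results is not known, because no skip rate is given. The 0.6 to 1.4 points, the 2 points and the 5% to 14% attenuation hold only under the skips assumed in steps 7 and 8.

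For the ANCOVA, the route to bias is a difference between arms at V3 or V5 in the number or true values of skipped items. The documents neither show nor exclude one, so the inference that the rule favours the intervention is not supported; the direction could be either. Nor can a departure from the instrument's scoring instructions be claimed, since these are not in the documents. The primary efficacy and safety analyses do not use the score; only their exploratory split at the MLHFQ median does.

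**What to change.** Before analysis:

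1. State in SAP 5.8.2 a minimum number of answered items below which the total is missing. Above it, score the mean of answered items × 21. Treat the physical and emotional sub-scores in the same way, each with its own number of items.
2. Name this in SAP 6.1 as an exception to the no-substitution rule.
3. Keep the raw-sum score and the complete-form score as sensitivity analyses of the ANCOVA.
4. Tabulate unanswered MLHFQ items by arm and visit.

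If the sponsor prefers to keep the raw sum, the table and the complete-form analysis are the least that is needed.

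The cost is two or three sentences, one scoring step and one table, assuming that the database holds the single items. There are two downsides. Forms below the minimum become missing; how many is unknown. And proration overstates the score, toward worse quality of life, if blanks truly mean 0: by k × m, which at m = 2.39 is 7.2 points for three blanks and 23.9 for ten. Ten blanks is what a minimum of half the items (11 of 21) would allow, so a stricter minimum limits this error. The number is the sponsor's choice; the documents do not supply one.

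A separate free improvement, not the correction of an error: compare PHQ-9 and self-estimated adherence between arms by ANCOVA with the baseline value as covariate, as already planned for the MLHFQ, instead of the t-tests in SAP 7.10.1.4 and 7.10.1.5. Baseline values are collected at V1. With equal variances and an assumed baseline-to-follow-up correlation r of 0.3, 0.5 or 0.7, the variance of the treatment estimate relative to a t-test on change is (1 + r)/2 = 0.65, 0.75, 0.85. Relative to a t-test on follow-up values it is 1 − r² = 0.91, 0.75, 0.51.
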